$\beta$ -hCG = Human chorionic gonadotropin-beta; BID = twice daily assessments; continuous = subsequent visits during the treatment period; COPD = chronic obstructive pulmonary disease; cont. = continuous; DNA = Deoxyribonucleic acid ; EDTA = Ethylenediaminetetraacetic acid ; EOS = End of Study; EOT = End of treatment; EQ-5D= Euro Quality of Life-5 Dimension questionnaire; EXACT = Exacerbations of COPD tool; FeNO = Fractional exhaled nitric oxide; HIV = human immunodeficiency virus; IgE = Immunoglobulin E; IMP = Investigational Medicinal Product; IVRS = Interactive Voice Response System; IWRS = Interactive Web Response System; LABA = Long-acting  $\beta_2$  agonists; LAMA = Long-acting muscarinic antagonist ; PARC = Pulmonary and activation-regulated chemokine; PGX = pharmacogenetic; PK = Pharmacokinetic; RNA = Ribonucleic acid; SABA = Short-acting  $\beta$ -agonists; SAEs = Serious adverse events; SC = subcutaneous; SGRQ = St. George's Respiratory Questionnaire.

- a Randomization/baseline Visit is defined as Day 1. The visit schedule should be adhered to within  $\pm 1$  week for the screening period,  $\pm 3$  days for the randomized IMP treatment period and  $\pm 5$  days for the post IMP treatment period.
- b All assessments at Visit 2 (Day 1) are to be conducted pre-IMP dose with the exception of the assessment of local tolerability of SC injections.
- c End-of-treatment visit: See [Section 7.1.1](#) for patients who discontinue treatment prematurely.
- d ECG to be centrally collected & read.
- e Chest X-ray to be performed unless a <6 month old chest x-ray/chest CT/chest MR is available. In case chest-X-ray is not feasible due to local regulations, magnetic resonance imaging (MRI) will be performed.
- f IMP (Dupilumab or placebo) is to be administered every 2 weeks by patient, caregiver or healthcare professional at the patient's home or in a health care facility. Last dose will be given at Week 50. After Week 8, if the patient or Investigator decides not to administer IMP at home, the IMP injections can be performed at the site by way of unscheduled visits. Patients will be monitored at the study site for a minimum of 30 minutes after injections. See [Section 6.1.1](#) for details.

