- g Electronic diary is used for recording of patient's answers to the EQ-5D-5L, EXACT and SGRQ questionnaires. This handheld device is dispensed at Screening Visit 1 (including instructions for use) and recorded information is reviewed on the other indicated days. At EOT visit the electronic diary is downloaded from the device and returned to the site.
- h Complete physical examinations will include skin, nasal cavities, eyes, ears, respiratory, cardiovascular, gastrointestinal, neurological, lymphatic, and musculoskeletal systems.
- i Vital signs, including systolic and diastolic blood pressure (mmHg), pulse rate (beats per minute), body temperature ( $^{\circ}$ C), and respiratory rate will be measured at screening, baseline and every subsequent on-site visit. Height (cm) will be measured at screening (Visit 1) only. Body weight (kg) will be measured at screening (Visit 1) and at EOT/EOS visits.
- j Hematology will include hemoglobin, hematocrit, platelet count, total white blood cell count, differential count, and total red blood cell count. Serum chemistry will include creatinine, blood urea nitrogen, glucose, lactate dehydrogenase, uric acid, total cholesterol, total protein, albumin, total bilirubin, alanine aminotransferase, aspartate aminotransferase, alkaline phosphatase, electrolytes (sodium, potassium, chloride), bicarbonate, and creatine phosphokinase. Urinalysis will include specific gravity, pH, glucose, ketones, blood, protein, nitrate, leukocyte esterase, urobilinogen and bilirubin. If any parameter on the dipstick is abnormal, a urine sample should be sent to the central laboratory for quantitative measurement. If positive for protein and/or red blood cells, microscopic analysis will be performed by the central laboratory.  

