The first part ("Symptoms") evaluates symptomatology, including frequency and severity of cough, sputum production, wheeze, breathlessness and the duration and frequency of attacks of breathlessness or wheeze. The second part has two components: "Activity" and "Impacts". The "Activity" section addresses disturbances to patients' daily physical activities. The "Impacts" section covers a range of effects that chest troubles may have on patients' daily life and psycho-social functions (eg daily life activities and functioning, employment, physical functioning, emotional impact, stigmatization, and patients' perceptions when treated). The recall period of the questionnaire is over the past 4 weeks.

Psychometric testing has demonstrated its repeatability, reliability and validity. Sensitivity has been demonstrated in clinical trials. A minimum change in score of 4 units was established as clinically relevant after patient and clinician testing (4, 5). The SGRQ has been used in a range of disease groups including asthma, COPD and bronchiectasis.

SGRQ is assessed at Visit 2 (Week 0), Visit 4 (Week 4), Visit 6 (Week 12), Visit 9 (Week 24), Visit 12 (Week 36), Visit 16 (Week 52) and Visit 19 (Week 64).

2.1.3.2.2 *Exploratory/Tertiary efficacy endpoints*

2.1.3.2.2.1 Exacerbations of chronic pulmonary disease tool (EXACT)

The EXACT tool quantifies and measures exacerbations of COPD and assesses the symptomatic manifestations of these COPD exacerbations (see Appendix D). The instrument is a daily diary composed of a total of 14 items representing the following domains:

- Breathlessness (5 items),
- Cough and sputum (2 items),
- Chest symptoms (3 items),
- Difficulty bringing up sputum (1 item),
- Tired or weak (1 item),
- Sleep disturbance (1 item), and
- Scared or worried (1 item).

The EXACT total score assesses COPD exacerbations. The higher the score, the more severe are the symptoms.

The EXACT questionnaire is assessed daily from screening to Visit 16 (Week 52). Baseline EXACT score as well as the post-baseline weekly scores will be calculated as the mean within-patient score over the prior 7 days, with data present for a minimum of 4 of the 7 days. If fewer

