than 4 days of data are available in the 7-day window, the EXACT score cannot be calculated and will be considered as missing. For the exacerbation analysis, the baseline would be reset during the study. Additional information related to computing scores and frequency, severity, and duration of events can be found in the user manual (6).

The Evaluating Respiratory Symptoms (E-RS) in COPD (E-RS: COPD) scale is a part of the EXACT tool. It is a derivative instrument used to measure the effect of treatment on the severity of respiratory symptoms in stable COPD. The E-RS utilizes the 11 respiratory symptom items contained in the 14-item EXACT.

The daily RS-Total score is computed by taking the sum of the 11 items comprising the instrument. It has a range of 0 to 40, with higher values indicating more severe respiratory symptoms.

The same summation procedure is used to derive the three daily domain scores:

- RS-Breathlessness (sum of items 7, 8, 9, 10, and 11; score range 0–17)
- RS-Cough and Sputum (sum of items 2, 3, 4; score range 0–11)
- RS-Chest Symptoms (sum of items 1, 5, 6; score range 0–12)

Like for EXACT, the baseline RS score as well as the post-baseline weekly domain and total scores are calculated as the mean within-patient score over the prior 7 days, with data present for a minimum of 4 of the 7 days. If fewer than 4 days of data are available in the 7-day window, the RS scores cannot be calculated and will be considered as missing.

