2.4.4.3 Multiplicity issues

The multiplicity procedure is proposed to control the overall type-I error rate for testing the primary and selected secondary endpoints listed below. The overall alpha is 0.05.

A non-binding futility interim analysis (IA) is planned in this study (details are provided in [Section 3](#)), and an administrative penalty of 0.001 will be taken from the significance level used at final analysis and thus two-sided 0.049 will be used. No further multiplicity adjustment will be performed for the IA.

At the final analysis, the comparisons with placebo will be tested based on the hierarchical order below at 2-sided $\alpha=0.049$.

1) Primary efficacy endpoints:

- Annualized rate of moderate or severe COPD exacerbations over the 52-week treatment period compared to placebo.

2) Secondary/exploratory efficacy endpoints:

- Change in pre-bronchodilator FEV1 from baseline to Week 12 compared to placebo
- Change in pre-bronchodilator FEV1 from baseline to Week 52 compared to placebo
- Change in pre-bronchodilator FEV1 from baseline to Week 12 compared to placebo in the subgroup of patients with baseline FENO ≥ 20 ppb
- Change in pre-bronchodilator FEV1 from baseline to Week 52 compared to placebo in the subgroup of patients with baseline FENO ≥ 20 ppb
- Change from baseline to Week 52 in SGRQ total score compared to placebo
- Proportion of patients with SGRQ improvement ≥ 4 points at Week 52 compared to placebo
- Change in E-RS COPD scores from baseline to Week 52 compared to placebo
- Annualized rate of moderate or severe COPD exacerbation compared to placebo over the 52-week treatment period in the subgroup of patients with baseline FENO ≥ 20 ppb

The study is considered positive when the primary endpoint achieves statistical significance.

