2.5.2 Data handling conventions for secondary efficacy variables

Periodical average of daily efficacy endpoints at designated study days

For the daily efficacy endpoints, the time period used to calculate the periodical average at each designated study day is summarized in [Table 5](#).

Randomization day is used as the reference day (Day 1).

Table 5 - Periodical average of daily efficacy assessment

Time point	EXACT, E-RS:COPD
Day 8 (Week 1)	2-8
Day 15 (Week 2)	9-15
Day 22 (Week 3)	16-22
Day 29 (Week 4)	23-29
Day 36 (Week 5)	30-36
Day 43 (Week 6)	37-43
...	...
Day 365 (Week 52)	359-365
...	...
Day 449 (Week 64)	443-449

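### SAP Table 5 fixes the Week 52 E-RS diary week at Days 359–365, but a permitted early Visit 16 (from Day 362) ends diary collection inside that week, so some on-schedule completers risk losing the score.

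*SAP*

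**What the plan says.** - **Diary week.** For the daily endpoints (EXACT and E-RS), SAP 2.5.2 states that "the time period used to calculate the periodical average at each designated study day is summarized in" Table 5. Randomization is Day 1, and Week 52 is Days 359–365. The window does not depend on when Visit 16 takes place.
- **Minimum data.** SAP 2.1.3.2.2.1 defines the weekly EXACT score as "calculated as the mean within-patient score over the prior 7 days, with data present for a minimum of 4 of the 7 days" and applies the same rule to E-RS: "If fewer than 4 days of data are available in the 7-day window, the RS scores cannot be calculated".
- **Visit window.** Protocol 1.3.1, footnote a, allows ±3 "days for the randomized IMP treatment period". SAP Table 7 gives Visit 16 a target of Day 365.
- **End of diary collection.** Protocol 1.3.1, footnote g: "At EOT visit the electronic diary is downloaded from the device and returned to the site". The schedule runs daily EXACT from screening to Week 52, and Protocol 8.1.2.1 says there is no daily recording in the post-treatment period.
- **Status of the endpoint.** SAP 2.4.4.3 places "Change in E-RS COPD scores from baseline to Week 52 compared to placebo" eighth of nine tests in the fixed sequence at two-sided 0.049, ahead of the exacerbation rate in the FeNO subgroup.
- **Analysis.** SAP 2.4.4.5.1 analyses weekly E-RS scores in a similar way to the Week 52 FEV1 analysis, that is, by MMRM.

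**The concern.** The averaging window is tied to the randomization date, while the end of data collection is tied to the visit date. When a permitted visit falls before Day 365, part of the Week 52 diary week lies after the patient has given up the device. A fully compliant patient seen on schedule can then have too few diary days for a Week 52 score, purely because of the appointment date.

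The SAP gives no fallback. A full 7-day run of entries before the visit does exist (Days 355–361 for a Day 362 visit), but Table 5 assigns Days 355–358 to Week 51. The other Week 52 measures are not exposed in this way: Table 7 allows Days 351–378 for pre-bronchodilator spirometry and Days 309–406 for SGRQ.

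At stake is precision for the eighth test in the hierarchy, which also gates the ninth.

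**Working it through.** **Inputs from the documents.** Randomization is Day 1; the minimum is 4 of 7 diary days; Visit 16 has a target of Day 365 ±3; the diary is returned at Visit 16.

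**Table 5 grid.** Target day = 7 × week + 1, and the window runs from target − 6 to target. Week 1 gives Days 2–8 and Week 52 gives Days 359–365, as in the SAP.

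**Visit 16 range.** 365 − 3 = 362 and 365 + 3 = 368.

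**Possible diary days in 359–365 for a visit on Day v.**
- Last entry the evening before: min(v − 1, 365) − 359 + 1.
- Entry on the visit day counted: min(v, 365) − 359 + 1.

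**Assumption for the probabilities.** Entries are independent, with a daily completion probability of 0.85. The documents give no such figure. P(missing) = P(Binomial(n, 0.85) ≤ 3), where n is the number of possible days, and equals 1 when n = 3.

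| Visit 16 day | Possible days, evening before | P(missing) | Possible days, visit-day entry | P(missing) |
|---|---|---|---|---|
| 362 | 3 | 1.000 | 4 | 0.478 |
| 363 | 4 | 0.478 | 5 | 0.165 |
| 364 | 5 | 0.165 | 6 | 0.047 |
| 365 | 6 | 0.047 | 7 | 0.012 |
| 366, 367, 368 | 7 | 0.012 | 7 | 0.012 |

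**Averaged over visit days** (the spread is also an assumption).
- Even spread, evening before: (1 + 0.478 + 0.165 + 0.047 + 3 × 0.012)/7 = 0.247. At 90% compliance it is 0.207, and at 80% it is 0.293.
- Even spread, visit-day entry: (0.478 + 0.165 + 0.047 + 4 × 0.012)/7 ≈ 0.106.
- Clustered on target, with weights 1-2-3-4-3-2-1 out of 16: 0.170 (evening before) and 0.067 (visit-day entry).
- Visits on Days 364–366 only, evening before: (0.165 + 0.047 + 0.012)/3 ≈ 0.07.
- Full 7-day window, any visit day: 0.012 at 85% compliance, 0.003 at 90%, 0.033 at 80%.

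**Effect on precision.** Suppose a fraction m of patients lacks Week 52 but has Week 51, and the correlation between the two weeks is ρ (an assumption). Using Week 51 alone as the supporting information, the variance at Week 52 is inflated by 1 + [m/(1 − m)](1 − ρ²).
- m = 0.25, ρ = 0.80: 1 + 0.333 × 0.36 = 1.12, or about 6% on the standard error.
- m = 0.25, ρ = 0.95: 1 + 0.333 × 0.0975 = 1.03, or about 2% on the standard error.

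**The case against.** A reader might infer that patients seen early in the window cannot have a Week 52 value at all. The documents do not support that. Under the 4-of-7 rule the score is impossible on only one of the seven permitted days, Day 362, and only if no entry is made that day. Visits on Days 363 and 364 leave 4 or 5 days even without a visit-day entry, so a score remains possible.

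Evening entry is stated only for controller medication (SAP 2.4.2.1.1); no time of day is given for EXACT or E-RS. Some text leans towards a visit-day entry: SAP 2.1.3.2.2.1 runs EXACT through Visit 16, and Protocol 8.1.2.1 puts questionnaires at a visit ahead of other procedures. If visit-day entries are made, no permitted visit day is excluded by rule.

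The ±3 days is a tolerance rather than a distribution, so every percentage depends on an assumed visit spread and an assumed compliance rate.

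The consequence is also limited. A completer without a Week 52 score still contributes all earlier weeks to the MMRM. E-RS sits late in the sequence under a secondary/exploratory label, is absent from the key secondary list in SAP 2.1.3.2, and does not decide whether the trial is positive.

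All of this stands, and it limits the size of the point. It does not remove the conflict between the fixed window and the return of the diary, for which the SAP states no rule.

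**Conclusion.** The conflict is real and the effect is modest. An on-schedule Visit 16 before Day 365 can truncate the Week 52 diary week: to 3 possible days (4 with a visit-day entry) on Day 362, with little slack on Days 363 and 364.

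Under the 85% compliance assumption, between about 7% and 25% of completers would lack a Week 52 score across the even and triangular spreads and the two entry times, against about 1% with a full week. Tighter clustering or better compliance lowers this further.

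A reader might also infer bias between the arms. Nothing in the documents points to it: the loss follows the appointment date in a double-blind trial. What remains is some loss of precision at an alpha-controlled time point, about 2–6% on the standard error in the 25% case under the assumed correlations. That makes this an inexpensive improvement to settle before unblinding. It does not threaten the trial's main conclusions.

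**What to change.** Add to SAP 2.5.2 and Table 5: when Visit 16 falls within Days 362–368, the Week 52 EXACT and E-RS scores use the 7 consecutive diary days ending on the last day of diary collection, capped at Day 365. The last day of collection is the visit day if an entry was made that day, and otherwise the day before. The 4-of-7 rule applies to those days. For these patients the Week 51 window ends the day before that diary week starts.

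The cost is a few sentences in the SAP and a small programming change, made without reference to treatment. There are two downsides to disclose:
- The Week 52 diary week moves earlier by up to 4 days (Days 355–361 for a Day 362 visit with no entry that day).
- Week 51, which is not a tested time point, is shortened. In that same case it keeps only Days 352–354, which is 3 days, so the Week 51 score is missing under the same rule.

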2.5.3 Missing data

For categorical variables, patients with missing data are not included in calculations of percentages unless otherwise specified. When relevant, the number of patients with missing data is presented.

Handling of computation of treatment duration if investigational medicinal product end of treatment date is missing

For the calculation of the treatment duration, the date of the last dose of IMP is equal to the date of last administration reported on the end-of-treatment case report form page. If this date is missing, the exposure duration should be left as missing.

The last dose intake should be clearly identified in the case report form and should not be approximated by the last returned package date.

Handling of medication missing/partial dates

No imputation of medication start/end dates or times will be performed. If a medication date or time is missing or partially missing and it cannot be determined whether it was taken prior or concomitantly, it will be considered a prior, concomitant, and posttreatment medication.

Handling of adverse events with missing or partial date/time of onset

Missing or partial adverse event onset dates and times will be imputed so that if the partial adverse event onset date/time information does not indicate that the adverse event started prior to treatment or after the treatment-emergent adverse event period, the adverse event will be classified as treatment-emergent. No imputation of adverse event end dates/times will be performed. These data imputations are for categorization purpose only and will not be used in listings. No imputation is planned for date/time of adverse event resolution.

Handling of adverse events when date and time of first investigational medicinal product administration is missing

When the date and time of the first IMP administration is missing, all adverse events that occurred on or after the day of randomization should be considered as treatment-emergent adverse events. The exposure duration should be kept as missing.

The last dose intake should be clearly identified in the case report form and should not be approximated by the last returned package date.

Handling of missing assessment of relationship of adverse events to investigational medicinal product

If the assessment of the relationship to IMP is missing, then the relationship to IMP has to be assumed and the adverse event considered as such in the frequency tables of possibly related adverse events, but no imputation should be done at the data level.

Handling of missing severity of adverse events

If the severity is missing for 1 of the treatment-emergent occurrences of an adverse event, the maximal severity on the remaining occurrences will be considered. If the severity is missing for all the occurrences, a “missing” category will be added in the summary table.

Handling of potentially clinically significant abnormalities

If a patient has a missing baseline he will be grouped in the category “normal/missing at baseline.”

For PCSAs with 2 conditions, one based on a change from baseline value or a normal range and the other on a threshold value, with the first condition being missing, the PCSA will be based only on the second condition.

For a PCSA defined on a threshold and/or a normal range, this PCSA will be derived using this threshold if the normal range is missing; eg, for eosinophils the PCSA is > 0.5 GIGA/L or $>ULN$ if $ULN \geq 0.5$ GIGA/L. When ULN is missing, the value 0.5 should be used.

Measurements flagged as invalid by the laboratory will not be summarized or taken into account in the computation of PCSA values.

2.5.4 Windows for time points

For the safety assessment, the reference date for the derivation of relative days of events or findings will be the date of first IMP administration. Selected safety variables will be summarized by the analysis window define in Table 6 for the by visit descriptive analysis. All available values from central lab will be assigned to the appropriate visit window. In the event of multiple measurements of the same test in the same window, the one closest to the targeted visit date will be used for the by-visit summary. If they are at the same distance to the target day, the latest one will be used. For procedures planned on Visit 2, if it is done on the same date as the first IMP injection but the performance time is missing, it will belong to Visit 2 time window.

Table 6 – Time window for safety endpoints

Visit	Target Day	Time windows for						
		Vital signs	Hema-tology, biochem-istry, urinalysis	Serum Pregnancy test, Hepatitis and HIV serology tests, height	Urine Pregnancy test	Physical examination	Body weight	ECG
Visit 1 (Week -4±1)	-28±7	<-14	<-14	1-		<-14	1-	<-14
Visit 2 (Week 0)	1	-14-1-	-14-1-		1-	-14-1-		-14-1-
Visit 3 (Week 2)	15	1+21						
Visit 4 (Week 4)	29	22-42	1+42		1+42			

Visit	Target Day	Time windows for						
		Vital signs	Hematology, biochemistry, urinalysis	Serum Pregnancy test, Hepatitis and HIV serology tests, height	Urine Pregnancy test	Physical examination	Body weight	ECG
Visit 5 (Week 8)	57	43-70	43-70		43-70			
Visit 6 (Week 12)	85	71-98	71-126		71-98			1+-126
Visit 7 (Week 16)	113	99-126			99-126			
Visit 8 (Week 20)	141	127-154			127-154			
Visit 9 (Week 24)	169	155-182	127-210		155-182	1+-266		127-210
Visit 10 (Week 28)	197	183-210			183-210			
Visit 11 (Week 32)	225	211-238			211-238			
Visit 12 (Week 36)	253	239-266	211-308		239-266			211-308
Visit 13 (Week 40)	281	267-294			267-294			
Visit 14 (Week 44)	309	295-322			295-322			
Visit 15 (Week 48)	337	323-350			323-350			
Visit 16 (Week 52)	365	351-378	309-406		351-406	267-406	1+-406	309-406
Visit 17 (Week 56)	393	379-406						

Visit	Target Day	Time windows for						
		Vital signs	Hematology, biochemistry, urinalysis	Serum Pregnancy test, Hepatitis and HIV serology tests, height	Urine Pregnancy test	Physical examination	Body weight	ECG
Visit 18 (Week 60)	421	407-434						
Visit 19 (Week 64)	449	>434	>406		>406	>406	>406	>406

1: up to 1st dose date/time; 1+: after 1st dose date/time;

For the efficacy assessment, the reference date for the derivation of relative days of events or findings will be the randomization day. If a patient receives IMP prior to the randomization by mistake, the reference date of efficacy assessment will be the date of the first IMP administration for that patient. For the primary analyses, all available values of scheduled measurements will be assigned to the appropriate visit window according to [Table 7](#). In the event of multiple measurements of the same test in the same window, the one closest to the targeted visit date will be used for the by-visit summary. If they are at the same distance to the target day, the latest one will be used.

Table 7 – Time window for efficacy variables

Visit	Target Day	Time windows for		
		Pre-bronchodilator Spirometry	Post-bronchodilator Spirometry	SGRQ
Visit 1 (Week -4±1)	-28±7	<-14	<-14	
Visit 2 (Week 0)	1	-14-1	-14-1	1
Visit 3 (Week 2)	15	1+-21	1+-21	
Visit 4 (Week 4)	29	22-42	22-42	1+-56
Visit 5 (Week 8)	57	43-70	43-70	
Visit 6 (Week 12)	85	71-98	71-126	57-126
Visit 7 (Week 16)	113	99-126		
Visit 8 (Week 20)	141	127-154		
Visit 9 (Week 24)	169	155-182	127-210	127-210
Visit 10 (Week 28)	197	183-224		
Visit 11 (Week 32)	225			
Visit 12 (Week 36)	253	225-280	211-308	211-308

Visit	Target Day	Time windows for		
		Pre-bronchodilator Spirometry	Post-bronchodilator Spirometry	SGRQ
Visit 13 (Week 40)	281			
Visit 14 (Week 44)	309	281-322		
Visit 15 (Week 48)	337	323-350		
Visit 16 (Week 52)	365	351-378	309-406	309-406
Visit 17 (Week 56)	393	379-406		
Visit 18 (Week 60)	421	407-434		
Visit 19 (Week 64)	449	>434	>406	>406

1-: up to randomization and before 1st dose date/time; 1+: after randomization or 1st dose date/time

For the pharmacokinetics/pharmacodynamics variables summary, the reference date for the derivation of relative days of measurements will be the date of first IMP administration if the patient is treated with study treatment, or the randomization date if the patient is not treated. Pharmacokinetics /pharmacodynamics variables will be summarized by the analysis window defined in [Table 8](#) for the by visit descriptive analyses. All available values of measurements will be assigned to the appropriate visit window. In the event of multiple measurements of the same test in the same window, the one closest to the targeted visit date will be used for the by-visit summary. If they are at the same distance to the target day, the latest one will be used. For procedures planned on Visit 2, if it is done on the same date as the first IMP injection but the performance time is missing, it will belong to Visit 2 time window.

Table 8 – Time window for pharmacokinetics/pharmacodynamics variables

Visit	Target day	Time windows for						
		FENO post-Bronchodilator	Serum dupilumab concentration	Anti-drug antibodies	Total IgE	PARC	Eotaxin-3	Fibrinogen
Visit 1 (Week -4±1)	-28±7							
Visit 2 (Week 0)	1	1-	1-	1-	1-	1-	1-	1-
Visit 3 (Week 2)	15		1+-21					
Visit 4 (Week 4)	29	1+-42	22-42				1+-56	
Visit 5 (Week 8)	57	43-70	43-70					
Visit 6 (Week 12)	85	71-126	71-98	1+-126	1+-224		57-126	
Visit 7 (Week 16)	113		99-140					
Visit 8 (Week 20)	141							
Visit 9 (Week 24)	169	127-210	141-210	127-266			127-266	1+-266
Visit 10 (Week 28)	197							
Visit 11 (Week 32)	225							
Visit 12 (Week 36)	253	211-308	211-308					

Visit	Target day	Time windows for						
		FENO post-Bronchodilator	Serum dupilumab concentration	Anti-drug antibodies	Total IgE	PARC	Eotaxin-3	Fibrinogen
Visit 13 (Week 40)	281							
Visit 14 (Week 44)	309							
Visit 15 (Week 48)	337							
Visit 16 (Week 52)	365	309-406	309-378	267-406	225-406	1*-406	267-406	267-406
Visit 17 (Week 56)	393		379-406					
Visit 18 (Week 60)	421		407-434					
Visit 19 (Week 64)	449	>406	>434	>406	>406	>406	>406	>406

1-: up to 1st dose date/time or randomization if patient is not treated; 1+: after 1st dose date/time or randomization date if patient is not treated;

